### Subject's assessment for Erythema

At its worst, how much abnormal redness of the skin on hands and feet have you had because of your condition during the last visit and this visit?

0 = none, 1 = minimal, 2 = moderate, 3 = severe, and 4 = very severe.

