### **6.7.2. Subject's Assessment for PPP Signs/Findings**

A part of PPSI assessment is used as a questionnaire. Skin lesion for the evaluation is the same as a palm or sole identified by Investigator for evaluation of PPSI at screening. This means the evaluated skin lesion site is the same with PPSI evaluation. Three signs of the disease (erythema, pustules/vesicle and desquamation/scale) are assessed by the subject him/herself, similar to PPSI. A numeric score is produced for each sign/finding of PPP and the range is from 0 to 4 and the total score will be 0 to 12.

A subject's assessment for each sign/finding on hands or feet (erythema, pustules/vesicles and desquamation/scale) are an exploratory disease-specific efficacy assessment. See [Appendix G](#). Worst status by a subject's own assessment between visits will be recorded.

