## APPENDIX G. SUBJECT'S ASSESSMENT - PPP SIGNS/FINDINGS FOR HANDS AND FEET

This assessment will be performed using the PPSI scoring system ([Appendix C](#)). A subject will evaluate skin lesion sites which are identified by either palms or soles, which has the most severe skin lesion assessed by an Investigator at screening. Any identified skin lesion site will be assessed at all subsequent visits by a subject.

Evaluation of skin lesion sites are assessed separately for erythema, pustules/vesicle and desquamation/scale, which are each rated on a scale of 0 to 4.

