4.2.4.3.1. AUC for PPSI total score

The AUC for PPSI total score is similarly defined as the AUC for PPPASI ([Section 4.2.4.1.2](#)).

4.2.4.4. Subject's assessment for each sign/finding of PPP (Erythema, Pustules/Vesicle and Desquamation/Scale of PPSI scale)

A subject's assessment for each sign/finding on hands or feet (erythema, pustules/vesicles and desquamation/scale) are an exploratory disease-specific efficacy assessment. Worst status by a subject's own assessment between visits will be recorded. A part of PPSI assessment is used as a questionnaire. A subject will evaluate skin lesion sites which has the most severe skin lesion assessed by an investigator for evaluation of PPSI at screening. Any identified skin lesion site will be assessed at all subsequent visits.

A numeric score is produced for each sign/finding of PPP and the range is from 0 to 4 (0 = none, 1 = minimal, 2 =moderate, 3 = severe, and 4 = very severe) and the total score will be 0 to 12.

CC-10004 (Apremilast)

Statistical Analysis Plan. Protocol CC-10004-PPP-001**4.2.4.5. PGA for palms and soles**

PGA for palms and soles is a physician's global assessment localized to palms and soles, which is skin lesions of PPP. Physician's global assessment is commonly used for assessment of the intervention. PGA for palms and soles also produces numeric score that can range from 0 to 5. A higher score indicates more severe disease.

Lesions on palms and soles will be graded based on the scales: 0 = Clear, 1 = Almost clear, 2 = Mild, 3 = Moderate, 4 = Severe, 5 = Very severe

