10.3.2. Continuous Variables

The continuous variables for secondary and exploratory endpoints in placebo-controlled phase include the following:

- AUC for PPPASI total score from baseline through Week 16
- PPPASI total score change from baseline at Week 16
- AUC for PPSI total score from baseline through Week 16
- PPSI total score change from baseline at Week 16
- AUC for modified PPPASI total score from baseline through Week 16
- Modified PPPASI total score change from baseline at Week 16
- Subject's assessment for PPP sign/finding (PPSI total score) at Week 16

The analysis of covariance (ANCOVA) model with treatment and stratification factor as the fixed effects, the associated baseline value as the covariate and multiple imputation (MI) method to impute the missing data will be applied. Within-group least-squares (LS) means, the associated standard error (SE), and treatment differences in LS means, the associated SE, and associated 2-sided 95% CIs and 2-sided p-values (nominal) will be derived from the model.

Missing value of at Week 16 will be imputed using the MI method ([SAS Institute Inc. 2015](#)) except for AUC. The SAS procedure MI will be used to impute missing scores to create M=100 complete data sets. The missing data patterns will be checked by treatment at baseline, and Week 2, 4, 6, 8, 10, 12, 14, and 16. If there are non-monotone missing patterns, following two separate imputation procedures will be used to complete the imputation process.

1. In the first step, the Markov Chain Monte Carlo (MCMC) method will be used to impute missing scores by treatment to create M=100 imputed data sets with monotone missing patterns. The minimum and maximum values for imputation will correspond to the lowest and the highest scores. The seed will be set at random, a single chain will be used to produce imputations. In case there are convergence issues, a simple model will be used to impute the

CC-10004 (Apremilast)

Statistical Analysis Plan. Protocol CC-10004-PPP-001

missing scores by treatment, with further simplification by dropping both treatment and stratification factor in imputation model if necessary.

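### The subject's sign assessment is defined on the investigator's PPSI site, but its three questions ask about hands and feet and never name that site

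*Protocol*

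**What the plan says.** Three places define the rated area as the investigator's PPSI site.

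- **Protocol 6.7.2:** "Skin lesion for the evaluation is the same as a palm or sole identified by Investigator for evaluation of PPSI at screening". It continues: "This means the evaluated skin lesion site is the same with PPSI evaluation".
- **Protocol Appendix G, introduction:** the subject is to use the site the investigator judged most severe at screening, and "Any identified skin lesion site will be assessed at all subsequent visits by a subject".
- **SAP 4.2.4.4:** "A subject will evaluate skin lesion sites which has the most severe skin lesion assessed by an investigator for evaluation of PPSI at screening".

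The questions printed in Appendix G differ. The erythema item asks "how much abnormal redness of the skin on hands and feet have you had because of your condition". The pustules/vesicle and desquamation/scale items likewise ask about the subject's hands and feet. No item names the index site or has a field for it, and the appendix title also says hands and feet.

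The three answers, each 0 to 4, are added to a 0 to 12 score that Appendix G calls the PPSI total score. SAP 10.3.2 keeps the label and lists the score among the Week 16 variables: "Subject's assessment for PPP sign/finding (PPSI total score) at Week 16". That analysis is an ANCOVA with multiple imputation and a nominal p-value. The score is also summarised by time point (SAP 10.3.2) and shown in shift tables (SAP 10.3.3). Protocol Table 2 and SAP Table 3 class the measure as exploratory.

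**The concern.** The definition and the instrument refer to different areas. A subject whose index site is the palms, and who also has disease on the soles, is asked a question that takes in both. If the form is used as printed, that subject may answer for the soles, for everything together, or for the palms alone, and the data will not show which. Different subjects may choose differently.

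At stake is the meaning of one exploratory patient-reported measure. A reader of the report who sees the PPSI label would take the score, and each of its three sign scores, as the subject's rating of the PPSI site.

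**Working it through.** The plan gives no figure for this measure, so the check is mainly a comparison of texts.

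**Step 1. Area declared and area asked about**

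| Place | Area |
|---|---|
| Protocol 6.4.2 and Appendix C (investigator's PPSI) | Palms or soles, whichever was most severe at screening |
| Protocol 6.7.2 | Same site as the PPSI; later in the section, hands *or* feet |
| Appendix G, introduction | Same site, kept at later visits |
| SAP 4.2.4.4 | Same site, kept at later visits |
| Appendix G, title | Hands *and* feet |
| Appendix G, all three items | Hands *and* feet |

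The mismatch affects all three items. All of this is current text; none of it comes from the amendment summary.

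**Step 2. How far the two areas differ**

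The weights in Protocol Appendix B are 20% for each palm and 30% for each sole. Protocol 6.4.2 can be read as one palm or sole, or as a pair, so both readings are shown.

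- Index site is one palm: 20%. One sole: 30%.
- Index site is both palms: 20% + 20% = 40%. Both soles: 30% + 30% = 60%.
- Area named in the items: 20% + 20% + 30% + 30% = 100%.

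The items therefore extend to a further 40% to 80% of the palmoplantar surface (100% − 60% to 100% − 20%). This measures area only. It is not an estimate of bias.

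**Step 3. Direction of any error in change from baseline**

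The documents do not say how a subject combines regions. As an assumption, let the answer be a mixture A = w·I + (1 − w)·O, where I is the rating the index site would get, O the rating the other regions would get, and w lies between 0 and 1. If w is the same at both visits, then

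ΔA − ΔI = (1 − w)(ΔO − ΔI).

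- With w = 1 (the subject rates only the index site) there is no error.
- If the other regions improve less than the index site, improvement at the index site is understated.
- If they improve more, it is overstated.

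Neither w nor ΔO − ΔI can be obtained from the protocol or SAP, so the size cannot be estimated.

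**Step 4. What depends on the score**

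The sample size rests on PPPASI-50 rates of 45% and 20%, which are investigator-rated. The investigator's PPSI, a secondary endpoint, has its own definition in Appendix C. Neither uses the subject's answers.

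**The case against.** The strongest reply is that the intended site is clear. The introduction to Appendix G stands directly above the items and says the subject rates the investigator's site, and staff could point to it. The trial is in Japanese subjects and the documents show only English wording, so the form as administered may name the site. This stands to the extent that one can say only that subjects *may* rate another area. It does not remove the contradiction: the introduction describes the subject in the third person, and no wording put to the subject names the site.

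It is also fair that the subject's score differs from the PPSI in other ways. The subject reports the worst status since the previous visit, a recall rule absent from Appendix C, and grade 1 is labelled minimal rather than slight. Correcting the site would not make the two scores interchangeable.

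Three stronger readings are tempting, and the documents do not support them.

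- **The items record the worst region, so the score can never be below the index-site score.** In these items, worst refers to time between visits (Protocol 6.7.2 and the Table 5 footnote). Nothing tells the subject to take a maximum over regions.
- **A planned comparison of subject with investigator is lost.** No section states that purpose, and SAP 10.3.2 and 10.3.3 plan no such comparison.
- **There are no scheduled Week 16 data.** In the text available for review, the Table 5 row for this assessment shows a dash at Week 16. That table is visibly broken, with some rows carrying 16 entries for 15 visits. Protocol Table 2 schedules the assessment at every double-blind visit and at Weeks 24 and 32, and 6.2.1 includes it at Week 32 or early termination.

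**Conclusion.** The point holds as a contradiction between the declared site and the questions asked. If the items were used as printed, the score labelled PPSI total score, and the three sign scores behind it, may not describe the PPSI site in subjects with disease elsewhere on the hands or feet. Change at the index site would be understated if other regions improve less. The documents give no basis for an amount.

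A reader might go on to infer that the treatment difference on this measure is diluted. That would require a smaller treatment effect outside the index site than on it, and neither document says so for this oral, systemic drug.

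The consequence is limited. The measure is exploratory and its p-values are nominal. Primary and secondary endpoints, alpha and sample size are untouched. The conclusion assumes that the administered form matches Appendix G and that no separate instruction directs subjects to the index site; neither can be checked from the documents. It is worth correcting because the text is wrong as it stands and the correction is cheap.

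**What to change.** **If the form can still be changed:** name the investigator's index site in each of the three Appendix G items, with the site pre-filled from screening, and bring the appendix title into line. State at the same time whether the site is one palm or sole or the pair, since Protocol 6.4.2 can be read either way.

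**If the items have already been used as printed:** leave the questionnaire alone. Redefine the measure as a hands-and-feet rating in Protocol 6.7.2, the Appendix G introduction and SAP 4.2.4.4, and drop the PPSI total score label from Appendix G and SAP 10.3.2.

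**Cost:** the first route needs three reworded items and a site field. Its drawback is that subject-rated signs outside the index site are no longer captured, although the investigator's PPPASI still covers all four regions. The second route needs text changes only, but gives up the same-site definition. Neither route changes the sample size or the analysis method.

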### Subject's assessment for Pustules/Vesicle

At its worst, how many blisters and/or inflamed bumps that are filled with pus on your hands and feet have you had because of your condition during the last visit and this visit?

0 = none, 1 = minimal, 2 = moderate, 3 = severe, and 4 = very severe.

### Subject's assessment for Desquamation/Scale

At its worst, how much peeling or shedding of skin and/or scabs on your hands and feet have you had because of your condition during the last visit and this visit?

0 = none, 1 = minimal, 2 = moderate, 3 = severe, and 4 = very severe.

The total score will be calculated by:

PPSI total score= (E + P + D)

Where E = erythema, P = pustular/vesicle and D = desquamation/scale

The total score ranges from 0 to 12

Reference: Modified from PPSI scoring system for the signs of the disease ([Appendix C](#)).

## APPENDIX H. DERMATOLOGY LIFE QUALITY INDEX (DLQI)

### DERMATOLOGY LIFE QUALITY INDEX

Hospital No: Date: DLQI  
Name: Score:   
Address: Diagnosis:

**The aim of this questionnaire is to measure how much your skin problem has affected your life  
OVER THE LAST WEEK. Please tick  one box for each question.**

1. Over the last week, how itchy, sore, painful or stinging has your skin been?	Very much 	A lot 	A little 	Not at all 	
2. Over the last week, how embarrassed or self conscious have you been because of your skin?	Very much 	A lot 	A little 	Not at all 	
3. Over the last week, how much has your skin interfered with you going shopping or looking after your home or garden?	Very much 	A lot 	A little 	Not at all 	Not relevant 
4. Over the last week, how much has your skin influenced the clothes you wear?	Very much 	A lot 	A little 	Not at all 	Not relevant 
5. Over the last week, how much has your skin affected any social or leisure activities?	Very much 	A lot 	A little 	Not at all 	Not relevant 
6. Over the last week, how much has your skin made it difficult for you to do any sport?	Very much 	A lot 	A little 	Not at all 	Not relevant 
7. Over the last week, has your skin prevented you from working or studying?	Yes 	No 			Not relevant 
	If "No", over the last week how much has your skin been a problem at work or studying?	A lot 	A little 	Not at all 	
8. Over the last week, how much has your skin created problems with your partner or any of your close friends or relatives?	Very much 	A lot 	A little 	Not at all 	Not relevant 
9. Over the last week, how much has your skin caused any sexual difficulties?	Very much 	A lot 	A little 	Not at all 	Not relevant 
10. Over the last week, how much of a problem has the treatment for your skin been, for example by making your home messy, or by taking up time?	Very much 	A lot 	A little 	Not at all 	Not relevant 

Please check you have answered EVERY question. Thank you.

© AY Finlay, GK Khan, April 1992 www.dermatology.org.uk, this must not be copied without the permission of the authors.

Finlay, 1994.

## APPENDIX I. EUROQOL 5 DIMENSION (EQ-5D)

**Health Questionnaire**

**English version for the UK**

UK (English) © 2009 EuroQol Group EQ-5D™ is a trade mark of the EuroQol Group

Under each heading, please tick the ONE box that best describes your health TODAY.

**MOBILITY**

I have no problems in walking about   
I have slight problems in walking about   
I have moderate problems in walking about   
I have severe problems in walking about   
I am unable to walk about

**SELF-CARE**

I have no problems washing or dressing myself   
I have slight problems washing or dressing myself   
I have moderate problems washing or dressing myself   
I have severe problems washing or dressing myself   
I am unable to wash or dress myself

**USUAL ACTIVITIES** (e.g. work, study, housework, family or leisure activities)

I have no problems doing my usual activities   
I have slight problems doing my usual activities   
I have moderate problems doing my usual activities   
I have severe problems doing my usual activities   
I am unable to do my usual activities

**PAIN / DISCOMFORT**

[figure not shown]
I have no pain or discomfort   
I have slight pain or discomfort   
I have moderate pain or discomfort   
I have severe pain or discomfort   
I have extreme pain or discomfort

**ANXIETY / DEPRESSION**

I am not anxious or depressed   
I am slightly anxious or depressed   
I am moderately anxious or depressed   
I am severely anxious or depressed   
I am extremely anxious or depressed

- We would like to know how good or bad your health is TODAY.
- This scale is numbered from 0 to 100.
- 100 means the best health you can imagine.  
0 means the worst health you can imagine.
- Mark an X on the scale to indicate how your health is TODAY.
- Now, please write the number you marked on the scale in the box below.

YOUR HEALTH TODAY =

## APPENDIX J. SAMPLE SERIOUS ADVERSE EVENT REPORT FORM

AMGEN CC-10004-PPP-001 Apremilast (Otezla)	Clinical Trial Serious Adverse Event Report – Phase 1-4 Notify Amgen Within 24 Hours of knowledge of the event Reminder: Enter the SAE information into RAVE and then send the paper Serious Adverse Event Report				 New  Follow-up																						
Report to Amgen Japan Safety - [contact]. If FAX is unavailable, email form to the following address: [contact]																											
1. SITE INFORMATION 
 
 Site Number	Investigator	County	Date of Report Day    Month    Year	
 
 				
 
 Reporter	Phone Number (       )	Fax Number (       )	
 
							Site Number	Investigator		County		Date of Report Day    Month    Year									Reporter			Phone Number (       )		Fax Number (       )	
Site Number	Investigator		County		Date of Report Day    Month    Year																						
Reporter			Phone Number (       )		Fax Number (       )																						
2. SUBJECT INFORMATION 
 
 Subject ID Number	Age at event onset	Sex  F  M	Race	If applicable, provide End of Study date	
 
 					
 
							Subject ID Number	Age at event onset		Sex  F  M	Race	If applicable, provide End of Study date															
Subject ID Number	Age at event onset		Sex  F  M	Race	If applicable, provide End of Study date																						
3. SERIOUS ADVERSE EVENT - Information in this section must also be entered on the AE/Serious Adverse Event Summary CRF Provide the date the Investigator became aware of this Serious Adverse Event Information: Day ____ Month ____ Year ____																											
Serious Adverse Event Diagnosis or Syndrome If diagnosis is unknown, enter signs / symptoms When Final Diagnosis is known, enter as Adverse Event  List one event per line. If event is fatal, enter the Cause of Death. Entry of "Death" is not acceptable, as this is an outcome.	Date Started  Day Month Year	Date Ended  Day Month Year	Check only if event occurred before first dose of IP (see codes below)	Enter Serious Adverse Event Code code (see codes below)	Relationship Is there a reasonable possibility that the event may have been caused by IP? If yes see section 10  Apremilast	Outcome of Event 01 Resolved 02 Not resolved 03 Fatal 04 Unknown																					
							No		Yes																		
Serious: 01 Fatal    03 Required hospitalization Criteria: 02 Immediately life-threatening    04 Prolonged hospitalization    05 Persistent or significant disability /incapacity    06 Congenital anomaly / birth defect    07 Other medically important serious event																											
4. HOSPITALIZATION 
 
 Date Admitted Day Month Year	Date Discharged Day Month Year	
 
							Date Admitted Day Month Year	Date Discharged Day Month Year																			
Date Admitted Day Month Year	Date Discharged Day Month Year																										
Was subject hospitalized or was a hospitalization prolonged due to this event?  No  Yes, If yes, please complete date(s):																											
5. INVESTIGATIONAL PRODUCT (IP) 
 
 	Initial Start Date  Day Month Year	Prior to, or at time of Event	Action Taken with Product	Lot # and Serial #	
 
 Date of Dose Day Month Year	Dose	Route	Frequency	
 
 Apremilast						           Lot # _____   Unknown            Serial # _____   Unknown         	
 
								Initial Start Date  Day Month Year	Prior to, or at time of Event				Action Taken with Product	Lot # and Serial #	Date of Dose Day Month Year	Dose	Route	Frequency	Apremilast						Lot # _____  Unknown Serial # _____  Unknown		
	Initial Start Date  Day Month Year	Prior to, or at time of Event				Action Taken with Product			Lot # and Serial #																		
		Date of Dose Day Month Year	Dose	Route	Frequency																						
Apremilast						Lot # _____  Unknown Serial # _____  Unknown																					
FORM-015482 Clinical Trial SAE Report – Phase 1-4 V 10.0 Effective date: 23-April-2018 Page 1 of 3							SAER Created: 09-April-2020																				

AMGEN CC-10004-PPP-001 Apremilast (Otezla)	Clinical Trial Serious Adverse Event Report – Phase 1–4 Notify Amgen Within 24 Hours of knowledge of the event Reminder: Enter the SAE information into RAVE and then send the paper Serious Adverse Event Report								 New  Follow-up		
		Site Number			Subject ID Number						
6. CONCOMITANT MEDICATIONS (eg. chemotherapy) Any Concomitant Medications?  No  Yes, If yes, please complete:											
Medication Name(s)		Start Date	Stop Date	Co-suspect	Continuing	Dose	Route	Freq.	Treatment M		
		Day	Month	Year	Day	Month	Year	No/✓	Yes/✓	No/✓	Yes/✓
7. RELEVANT MEDICAL HISTORY (include dates, allergies and any relevant prior therapy)											
8. RELEVANT LABORATORY VALUES (include baseline values) Any Relevant Laboratory values?  No  Yes, If yes, please complete:											
Date Day    Month    Year	Test Unit										
9. OTHER RELEVANT TESTS (diagnostics and procedures) Any Other Relevant tests?  No  Yes, If yes, please complete:											
Date Day    Month    Year		Additional Tests				Results				Units	

## APPENDIX K. PREGNANCY NOTIFICATION FORM

Amgen Proprietary - Confidential

Report to Amgen Japan Safety at: [contact]. If FAX is unavailable, email form to: [[contact]](mailto:[contact])

### 1. Case Administrative Information

Protocol/Study Number: CC-10004-PPP-001 (Apremilast/Otezla)

Study Design:  Interventional  Observational (If Observational:  Prospective  Retrospective)

